6.13.7. Immunogenicity

An individual sample is potentially examined multiple times in a hierarchical procedure to produce a sample anti-drug antibodies (ADA) assay result and potentially a sample neutralizing anti-drug antibodies (NAb) assay result. A patient has treatment-emergent anti-drug antibodies (TE-ADA) when ADA are induced or boosted by exposure to study drug; i.e., when at least one postbaseline ADA sample has a 4-fold increase in titer, compared to baseline (if ADA were present at baseline) or has a titer 2-fold greater than the minimum required dilution of 1:10 (if no ADA were present at baseline).

Compound level safety standards will be followed in the analyses of immunogenicity. Listings of immunogenicity assessments will be provided-along with the summary of specified TEAEs by TE ADA status. The summary of TE ADA and NAb status will be produced for all 3 safety populations, where the post baseline period for reporting is the same as described for AEs in Section 6.13.2. For the Re-randomized Maintenance population the analysis of TEAEs will be cumulative across both the Induction and Maintenance Periods. Additional assessments of the relationship between immunogenicity and efficacy will be performed as part of the integrated analysis including other Phase 3 mirikizumab psoriasis trials.

6.13.8. Special Safety Topics including Adverse Events of Special Interest

This section includes areas of interest, whether due to observed safety findings, potential findings based on drug class, or safety topics anticipated to be requested by a regulatory agency for any reason. In general, potential adverse events of special interest (AESI) relevant to these special safety topics will be identified by one or more standardized MedDRA query(ies) (SMQs),

by a Lilly defined MedDRA PT listing, based upon the review of the most current MedDRA Version, or by treatment-emergent relevant laboratory changes, as described below. Additional special safety topics may be added, as warranted.

Unless otherwise specified, the AESIs will be summarized for all three safety populations during their associated study periods using the baseline and postbaseline definitions described in Sections 6.13.2 and 6.13.4.

Full details of the search terms and rules for deriving AESIs in each of the sections below are described in the compound level safety standards along with information about the types of summaries and listings to be provided.

6.13.8.1. Hepatic Safety

Hepatic laboratory tests include alanine aminotransferase (ALT) and aspartate aminotransferase (AST), total bilirubin (TBL) and serum alkaline phosphatase (ALP). When criteria are met for hepatic evaluations, investigators will complete a follow-up hepatic safety eCRF.

Analyses will include:

- ALT and AST: The percentages of patients with a measurement greater than or equal to 3 times (3X), 5 times (5X), and 10 times (10X) the Covance upper limit of normal (ULN) during the treatment period for all patients with a postbaseline value and for subsets based on various levels of baseline value.
- TBL and ALP: The percentages of patients with a measurement greater than or equal to 2 times (2X) the Covance ULN during the treatment period will be summarized for all patients with a postbaseline value and for subsets based on various levels of baseline value.
- Plot of maximum postbaseline ALT versus maximum postbaseline total bilirubin (entire safety population).
- A listing of the information collected on the hepatic-safety eCRF.

6.13.8.2. Infections, Including Opportunistic Infections and Serious Infections

Infections will be defined using the PTs from the MedDRA Infections and Infestations SOC. Treatment-emergent infections will be analyzed for: all infections (by maximum severity), serious infections and opportunistic infections (OI). The MedDRA terms used to identify infections considered to be OI in patients with immune mediated inflammatory conditions treated with immunomodulatory drugs are based on Winthrop et al. (2015) and are listed in the compound level safety standards. The list contains narrow (more specific) and broad (less specific) PTs with respect to these prospectively defined opportunistic infections.

Analyses will include:

- Infections/Serious Infections: treatment-emergent infections by PT.
- Opportunistic Infections: treatment-emergent OI by narrow terms and broad terms separately.

6.13.8.3. Hypersensitivity

Hypersensitivity reactions is used as an overarching term to describe events that are systemic or localized reactions that likely have an allergic/hypersensitivity etiology. Patients will be evaluated by the investigator for signs and symptoms suggestive of hypersensitivity, and investigators will complete a follow-up eCRF designed to record additional information.

Potential hypersensitivity reactions will be determined using the following SMQs: anaphylactic reaction, hypersensitivity, and angioedema. Potential hypersensitivity will be categorized as Immediate (i.e., occurring within 24 hours) and non-immediate (i.e., occurring after the day of study drug administration but prior to subsequent drug administration), based on the timing of the reaction.

Analyses will include:

- For Immediate Hypersensitivity: (1) combined narrow/algorithmic search (i.e. any narrow term from any one of the SMQs, or anaphylaxis algorithm), (2) narrow search (i.e. any narrow term) by SMQ, (3) broad search (i.e. any narrow or broad term) by SMQ, and (4) TEAEs (occurring on the day of study drug administration) by PT not in any of the 3 SMQs
- For Non-Immediate Hypersensitivity: (1) combined narrow search (i.e. any narrow term from any one of the SMQs), (2) narrow search (i.e. any narrow term) by SMQ, and (3) broad search (i.e. any narrow or broad term) by SMQ

CCI

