7.1. Treatments Administered

This study involves evaluation of mirikizumab (250 mg or 125 mg) and placebo administered SC during 52 weeks of double-blind treatment. [Table AMAK.3](#) shows the treatment regimens.

Table AMAK.3. Treatment Regimens

Regimen Group	Dosing	Description
250 mg miri Q4W		
At W0, 4, 8, and 12 for patients randomized to mirikizumab during the Induction Period
 
At W16, 20, 24, 28 and 32 of the Maintenance Period, for patients who were randomized to placebo during the Induction Period

250 mg miri Q8W		During the Maintenance Period only, starting at W16
125 mg miri Q8W		During the Maintenance Period only, starting at W16
Placebo		
At W0, 4, 8, and 12 for patients randomized to placebo during the Induction Period
 
At all visits during the Maintenance Period, as necessary, to maintain the study blind across treatment groups

Abbreviations: miri = mirikizumab; CCI; Q4W = every 4 weeks; Q8W = every 8 weeks; W = Week.

Detailed instructions for investigational product administration will be provided by the Sponsor, and the investigational product will be administered at the site by clinical staff.

The investigator or his/her designee is responsible for the following:

- Explaining the correct use of the investigational agent(s) to the site personnel,
- Verifying that instructions are followed properly,
- Maintaining accurate records of investigational product dispensing and collection,
- At the end of the study returning all unused medication to Lilly, or its designee, unless the Sponsor and sites have agreed all unused medication is to be destroyed by the site, as allowed by local law.

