7.2.1. Selection and Timing of Doses

Study visits at which investigational product is administered are preferred, if possible, to occur on the same day of the week. In any case, the study visits should occur within the visit window specified on the Schedule of Activities (see Section 2). The actual time of all dose administrations will be recorded in the patient's electronic case report form (eCRF).

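### SAP 6.13.8.3 sets Immediate hypersensitivity by elapsed hours and Non-immediate by calendar day, so a next-day reaction within 24 hours of the injection meets both definitions

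*SAP*

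**What the plan says.** SAP 6.13.8.3 states: "Potential hypersensitivity will be categorized as Immediate (i.e., occurring within 24 hours". In the same sentence it describes Non-immediate events as those "occurring after the day of study drug administration but prior to subsequent drug administration". Events are assigned "based on the timing of the reaction", and no order of precedence is given.

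The section then lists the analyses:

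- **Immediate, four items:** (1) a combined search on narrow terms or the anaphylaxis algorithm; (2) a narrow search by SMQ; (3) a broad search by SMQ; (4) "TEAEs (occurring on the day of study drug administration) by PT not in any of the 3 SMQs".
- **Non-immediate, three items:** (1) a combined search on narrow terms only; (2) a narrow search by SMQ; (3) a broad search by SMQ. There is no algorithm and no counterpart to item (4).

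The parent section, SAP 6.13.8, adds: "Full details of the search terms and rules for deriving AESIs in each of the sections below are described in the compound level safety standards".

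**The concern.** A two-way split by timing should place each reaction in one category. Here the upper limit of one category is measured in hours and the lower limit of the other in calendar days. The two limits coincide only for an injection at midnight.

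Hypersensitivity, including anaphylaxis, is listed as an adverse event of special interest in Protocol 9.2.3, and SAP 6.13.8 has such events summarised for all three safety populations. The boundary applies after every injection: Weeks 0, 4, 8 and 12, then every 4 weeks from Week 16 to Week 48, which is 4 + 9 = 13 dosing visits for a patient who completes treatment. Two programmers working from the SAP alone could reasonably produce different Immediate and Non-immediate counts from the same data.

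**Working it through.** The plan gives no figure to reproduce. The check applies the two rules literally.

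**Inputs**

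- Immediate: elapsed time since the dose of 24 hours or less (SAP 6.13.8.3).
- Non-immediate: onset on a calendar day after the dosing day and before the next dose (SAP 6.13.8.3).
- Injection clock time: not given. The Protocol says only that "the investigational product will be administered at the site by clinical staff" (Protocol 7.1). I assume 08:00 to 17:00.

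**Overlap.** For an injection at clock hour h, midnight falls 24 − h hours after the dose. Both rules hold from 24 − h to 24 hours after the dose, a span of 24 − (24 − h) = h hours.

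| Injection | Both rules met (hours after dose) | Length | Share of the 24 hours |
|---|---|---|---|
| 08:00 | 16 to 24 | 8 h | 8/24 = 33% |
| 10:00 | 14 to 24 | 10 h | 10/24 = 42% |
| 14:00 | 10 to 24 | 14 h | 14/24 = 58% |
| 17:00 | 7 to 24 | 17 h | 17/24 = 71% |

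These are shares of clock time under the assumed hours, not shares of events. There is no gap: any onset more than 24 hours after the dose is necessarily on a later calendar day.

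**Single cases**

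- Injection 14:00, onset 08:00 next day: 24 − 14 + 8 = 18 hours. Meets both definitions.
- Injection 10:00, onset 08:00 next day: 24 − 10 + 8 = 22 hours. Meets both.
- Injection 08:00, onset 09:00 next day: 24 − 8 + 9 = 25 hours. Non-immediate only.

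**What the boundary changes.** Take the 18-hour reaction:

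- *Coded to a narrow SMQ term.* It is found under either rule. Only its placement changes: Immediate under the 24-hour rule, Non-immediate under the calendar-day rule, and both if each definition is applied as printed.
- *Qualifying only through the anaphylaxis algorithm.* Under the 24-hour rule it enters the Immediate combined search. Under the calendar-day rule it enters neither combined search. The SAP does not describe the algorithm, so whether the event would still surface in a broad search cannot be said.
- *Outside all three SMQs.* As printed, it appears in none of these tables, because item (4) is limited to the dosing day and Non-immediate has no such item. If 24 hours governed all four Immediate items, it would appear in item (4).

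**One boundary for both categories and item (4)** reduces the overlap to 0 hours, whichever boundary is chosen.

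**The case against.** The strongest reply is that a calendar-day split was meant all along. The Non-immediate definition and item (4) are exact calendar-day complements, and sorting by the timing of the reaction suggests one category per event. On that view the 24-hour phrase is a loose gloss for the dosing day. This is plausible, and it supports the choice of fix. It does not remove the conflict, because the 24-hour phrase is the only printed definition of Immediate and items (1) to (3) inherit it.

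The second reply is that the compound level safety standards hold the full derivation rules and may already settle the matter. That stands as a limit on the finding. A reader might infer that events will be double counted; the supplied documents do not show this. They show only that the SAP wording allows it.

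The third reply is that the consequence is small. SAP 6.13.2 has adverse event tables count patients and asks for caution with p-values because multiplicity is not controlled. SAP 6.13.8.3 lists no pooled Immediate-plus-Non-immediate total that could be inflated. That also stands.

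**Conclusion.** The SAP's timing definitions conflict for a reaction on the next calendar day that starts within 24 hours of the injection, and items (1) to (3) and item (4) of the Immediate analyses use different boundaries. No rule in the supplied documents resolves this. The choice of boundary affects which events are captured, because the algorithm and item (4) apply only to Immediate events.

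The size is minor. Only safety tables for one event of special interest are affected; no primary or multiplicity-controlled analysis is. The number of events involved cannot be derived from the documents.

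Two further inferences should be avoided. Not every next-morning reaction is ambiguous: one beyond 24 hours is Non-immediate only. And the 33% to 71% of clock time is not a proportion of events. It rests on assumed clinic hours, and reading it as events would require onsets spread evenly over 24 hours, which nothing in the documents supports.

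**What to change.** Use one boundary for both categories and for item (4). For example:

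- **Immediate:** onset on the calendar day of study drug administration, after the dose.
- **Non-immediate:** onset on any later day before the next administration.

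Replace the 24-hour phrase accordingly and align the text with the compound level safety standards. This matches item (4) and the existing Non-immediate wording, and no onset time is needed to separate a dosing-day event from a later-day one. A time is still needed to tell whether a dosing-day event came before or after the injection, so add a rule for a missing onset time on dosing days. SAP 6.13.2 already has one for the first dosing day: assume the later period.

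The alternative is 24 hours throughout. Dose times would support it (Protocol 7.2.1: "The actual time of all dose administrations will be recorded in the patient's electronic case report form (eCRF"), but every next-day event would then need an onset time, and SAP 6.13.2 expects some start times to be missing.

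The cost is a sentence or two in the SAP and no new data collection. The downside of the calendar-day rule is that a next-day reaction within 24 hours is classed as Non-immediate, and so falls outside the algorithmic search and item (4) as those are now listed.

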6.13.8.5. Cerebro-Cardiovascular Events

The cerebro-cardiovascular events reported in the study will be adjudicated by an independent, external adjudication committee (AC). All confirmed events after adjudication will be used for the analysis of cerebro-cardiovascular events. Categories of events include: Cardiovascular, Neurologic, and Peripheral Vascular Events. As detailed in the compound level safety standards, the categories are further categorized into subcategories.

Analyses will include:

- Treatment-emergent cerebro cardiovascular confirmed events by category, subcategory, and PT.
- By-patient listing for all patients having a TEAE of cerebro-cardiovascular (confirmed event, no event, or insufficient documentation for event determination), at any time.

6.13.8.6. Malignancies

Malignancies will be defined using PTs from the Malignant tumors SMQ. Malignant tumor events will be summarized separately for the categories: Non-Melanoma skin cancer (NMSC) and Malignancies, excluding NMSC.

Analyses will include:

- Treatment-emergent malignancy by category and PT.
- By-patient listing for all patients having a TEAE of malignancy at any time.

6.13.8.7. Suicidal Ideation/Behavior and Depression

During the study, suicidal ideation and behavior, and depression will be assessed prospectively by the investigator via signs and symptoms and through the use of the Columbia-Suicide Severity Rating Scale (C-SSRS) and the Quick Inventory of Depressive Symptomatology – Self Report (QIDS-SR16).

Analyses will include:

- C-SSRS: Only a listing of the C-SSRS will be provided. Additional summaries may be provided if justified by the number of events (further described in the compound level safety standards).
- QIDS-SR16: Shift tables will be provided showing the number and percentage of patients within each baseline category (maximum value) versus each postbaseline category (maximum value) by treatment. Additionally, outcomes such as any increase in depression will be compared between treatments (further described in the compound level safety standards).

CCI

6.14.2. Safety Subgroup Analyses

Subgroup analysis for safety related endpoints will be performed within the context of the integrated safety analysis. No safety subgroup analysis will be performed specifically for this study, unless there is a potentially relevant finding during the periodic study safety reviews.

6.15. Analysis for Japan Submission

A subset of the planned efficacy, health outcomes and safety analyses will be reproduced based on patients from Japan sites, in support of the regulatory submission in Japan. The list of tables, listings, and figures for the patients from Japan sites (Japanese population) will be in a separate document.

6.16. Analysis for Australian Submission

In addition to the analysis already specified, efficacy analysis will be conducted to meet the Pharmaceutical Benefits Advisory Commission (PBAC) criteria. The PBAC population is a subset of the patients with a PASI score >15 at baseline in the induction ITT and Re-randomized Maintenance ITT Populations. The sPGA (0,1), sPGA (0), PASI 75, PASI 90 and PASI 100 using the PBAC population will be analyzed.

6.17. Protocol Deviations

Protocol deviations will be identified throughout the study. Important protocol deviations are defined as those deviations from the protocol likely to have a significant impact on the completeness, accuracy, and/or reliability of the study data or that may significantly affect a patient's rights, safety, or well-being.

As specified in [Table AMAK.6.1](#), the Induction PPS population is defined as all randomized patients who do not have important protocol deviations excluded from per protocol analysis (IPDPP) in the induction period. A separate document known as the "The AMAK Trial Issues Management Plan" describes the categories and subcategories of important protocol deviations, the action to be taken regarding the exclusion of patients from PPS, and the source of the deviation identified.

The number and percentage of patients having important protocol deviation(s) will be summarized within category and subcategory of deviations by treatment for the Induction ITT population and for the Maintenance ITT population.

A by-patient listing of important protocol deviations will be provided.

6.18. Interim Analyses and Data Monitoring

Data Monitoring Committee (DMC): One DMC, consisting of members external to Lilly, will be established for interim safety monitoring across Studies I6T-MC-AMAK, I6T-MC-AMAJ and I6T-MC-AMAH in patients with psoriasis. This committee will consist of a minimum of 3 members, including a physician with expertise in dermatology and a statistician. No member of the DMC may have contact with study sites. A Statistical Analysis Center (SAC) will prepare and provide unblinded safety data to the DMC. The SAC members may be Lilly employees or from third-party organizations designated by Lilly. However, they will be external to the study team and will have no contact with sites and no privileges to influence change in the ongoing study. Access to the unblinded safety data will be limited to the DMC and the SAC or their designees. The study team will not have access to the unblinded data. Only the DMC is authorized to evaluate unblinded data. The purpose of the DMC is to advise Lilly regarding continuing patient safety; however, the DMC may request key efficacy data to put safety observations into context and to confirm a reasonable benefit/risk profile for ongoing patients in the study. Hence, there will be no alpha adjustment for these interim assessments. Study sites will receive information about interim assessments ONLY if they need to know for the safety of their patients. This committee will make recommendations as to whether it is scientifically and ethically appropriate to continue enrollment, discontinue a treatment group, or discontinue the study. Details outlining the roles and responsibilities of the DMC will be finalized in the DMC charter and an associated DMC analysis plan prior to the first unblinded assessment.

Week 16 (Primary Endpoint) Database Lock: A limited number of Lilly employees or their designees *not in direct contact with the clinical sites* may be provided access to the data from this study once all randomized patients either complete the assessments for primary endpoints at Week 16 (Visit 7) or discontinue from the study. The purpose of providing this access to a small group is to initiate work related to regulatory submission upon completion of the study. The study will not be terminated prematurely on the basis of either efficacy or futility following the Week 16 interim analysis. Although this is an interim analysis with respect to the entire study, it is the only and final analysis for the primary endpoint. Therefore, no alpha adjustment for this interim analysis is planned.

Week 52 Database Lock: An unblinded analysis will be performed after all patients have completed the Week 52 Visit or discontinued study treatment. This database lock will include all data collected by the cut-off date including follow-up data from patients that have begun Post-Treatment Follow-Up Period. This is the final analysis for the efficacy endpoints up to Week 52. However, the study may be ongoing for the Post-Treatment Follow-Up Period at the time of this database lock.

Final Database Lock: A final database lock will occur after the Post-Treatment Follow-Up Period is completed.

6.19. Annual Report Analyses

Based on regulatory requirements for the Development Safety Update Report (DSUR), reports will be produced (if not already available from the study CSR) for the reporting period covered by the DSUR.

6.20. Clinical Trial Registry Analyses

Additional analyses will be performed for the purpose of fulfilling the Clinical Trial Registry (CTR) requirements.

Analyses provided for the CTR requirements include the following:

Summary of AEs, provided as a dataset which will be converted to an XML file. Both SAEs and “Other” AEs are summarized by treatment group, by MedDRA preferred term.

- An AE is considered “Serious,” whether or not it is a TEAE.
- An AE is considered in the “Other” category if it is both a TEAE and is not serious. For each SAE and “Other” AE, for each term and treatment group, the following are provided:
 - the number of participants at risk of an event
 - the number of participants who experienced each event term
 - the number of events experienced.
- Consistent with www.ClinicalTrials.gov requirements, “Other” AEs that occur in fewer than 5% of patients/subjects in every treatment group may not be included if a 5% threshold is chosen (5% is the minimum threshold).
- AE reporting is consistent with other document disclosures for example, the CSR, manuscripts, and so forth.

7. Unblinding Plan

Unblinding details are specified in a separated unblinding plan.

8. References

- Agresti A. *Categorical Data Analysis*. 3rd ed. Hoboken, NJ: John Wiley & Sons; 2013.
